4.2 SCIENTIFIC RATIONALE FOR STUDY DESIGN AND JUSTIFICATION FOR DOSE

Several studies have shown the efficacy of lower frequency stimulation, defined anywhere from 60-80Hz of the STN, in treating gait dysfunction and freezing that develop years later among chronic DBS patients (7-12). We reported that 60Hz stimulation could be utilized and beneficial within the first year of implantation for a small number of patients with significant gait disorder (12). We also showed that stimulation through the ventral contacts was utilized in all patients with relatively modest changes achieved in levodopa equivalent daily dose. Building upon this result, we performed a systemic analysis to determine whether a clinical pattern exists among subjects that benefited most from certain stimulation frequencies (38). The team analyzed preoperative MDS-UPDRS III scores (32 indicators) collected from 20 PD patients implanted with STN-DBS on either 60 Hz stimulation (ten patients) or HFS (130–185 Hz) (ten patients) for an average of 12 months. The goal was to apply machine learning to accurately “classify” patients into their corresponding optimal stimulation frequency group using a subset or all of the patient-specific indicators collected preoperatively. Machine learning algorithms are of two main types, namely, supervised and unsupervised algorithms. Supervised learning algorithms require ground truth (e.g., direct measurements or observations) for the data used in training and testing, whereas unsupervised learning algorithms do not require ground truth and are typically used to

group the data into clusters with respect to their similarities. In supervised learning, the task of estimating the ground truth for a new observation is generally referred to as making a “prediction.” Predicting ground truths of categorical type is typically referred to as “classification,” and predicting ground truths of continuous type is generally referred to as “regression.” In our prior work, we developed a novel supervised machine learning model based on random forest method that was able to classify patients into subgroups with 95% accuracy and determined that gait and rest tremor of the right hand were consistently the most important factors to the classification.

4.3 END OF STUDY DEFINITION

A participant is considered to have completed the study if he or she has completed all phases of the study including the last visit or the last scheduled procedure shown in the Schedule of Activities (SoA), Section 1.3.

5 STUDY POPULATION

5.1 INCLUSION CRITERIA

In order to be eligible to participate in this study, an individual must meet all of the following criteria:

1. Provision of signed and dated informed consent form
2. Stated willingness to comply with all study procedures and availability for the duration of the study
3. Male or female, aged 21-80
4. Patients diagnosed with Parkinson's disease (PD) (Hughes 1992)
5. PD subjects who have bilateral STN-DBS (greater than 3 months) or in the preoperative stage of being implanted with bilateral STN-DBS
6. Have underlying gait disorder defined as a score of 2 or more on the gait sub-score of the MDS-UPDRS III in the levodopa-OFF state
7. Currently treated with oral levodopa therapy

5.2 EXCLUSION CRITERIA

An individual who meets any of the following criteria will be excluded from participation in this study:

1. Cognitive deficits based on historical record that limit participant compliance with study protocol
2. Vestibular disorder or musculoskeletal problems affecting gait or balance

5.3 SCREEN FAILURES

Screen failures are defined as participants who consent to participate in the clinical trial but are not subsequently entered in the study. A minimal set of screen failure information is required to ensure transparent reporting of screen failure participants, to meet the Consolidated Standards of Reporting Trials (CONSORT) publishing requirements and to respond to queries from regulatory authorities. Minimal information includes demography, screen failure details, eligibility criteria, and any serious adverse event (SAE).

Individuals who do not meet the criteria for participation in this trial (screen failure) because of decompensation of their Parkinson's disease due to other medical issues or acute musculoskeletal problems may be rescreened after they have returned to their baseline physical state. Rescreened participants should be assigned the same participant number as for the initial screening.

5.4 STRATEGIES FOR RECRUITMENT AND RETENTION

Subjects will be recruited from *the Neurology Parkinson's and Movement Disorders Division at Northwell Health* and from local physicians within and outside of Northwell Health. Outreach will include recruitment databases such as [but not limited to] Fox Trial Finder, CenterWatch, The Parkinson Alliance, Northwell E-news bulletin and the Northwell Health Clinical Trials webpage. For participants recruited outside of Northwell Health, medical records will be required to confirm eligibility. Participant screening and recruitment will then be conducted by the Lead Principal Investigator and research coordinator. Retention of participants will be maintained through thoroughness by the lead principal investigator and research coordinator.

6 STUDY INTERVENTION

6.1 STUDY INTERVENTION(S) ADMINISTRATION

6.1.1 STUDY INTERVENTION DESCRIPTION

Deep Brain Stimulation Programming

Parkinson's patients who will be undergoing STN-DBS implantation or who have chronic bilateral STN-DBS will be eligible to participate. Each electrode contact will be reprogrammed by the Lead Principal Investigator in both low frequency and HFS. For each of the 4 contacts on both electrodes, the amplitude will be slowly increased by 0.1-V increment until sustained sensory or motor side effects are produced in HFS. The amplitude below the side effect threshold will be used along with a standard pulse width of 60 μ s.

Inertial Sensors:

Participants will also be outfitted with the full body Opal sensors (APDM, Opal, and Portland, OR) affixed to the wrists, feet, sternum and lumbar spine (L5 level) and the Kinesia inertial sensors (Great Lakes Technologies, OH) that will be affixed to their finger and ankle. For the gait analysis, the Mobility Lab System (APDM, Portland, OR) will be used. It includes both ambulatory PD monitoring as well as expansive analytical software that measures outcomes from watch size sensors that are tethered to various body regions by Velcro bands. Each sensor acquires 3-D linear acceleration, angular velocity and magnetic field information for directional orientation from accelerometers, gyroscopes, and magnetometers, respectively (48). The sensor data is wirelessly streamed to a laptop where Mobility Lab software will generate the gait and balance metrics. iSway and iTUG are two of the modules within the software system. iTUG's gait calculations, including stride length, velocity, cadence, trunk movements, turning, and turn to sit, were deemed to be most reliable and correlated well to the UPDRS III (49). iSWAY has also been validated to measure dynamics of postural control (50).

The Kinesia One (Great Lake Neurotechnologies, Cleveland, OH) sensor incorporates both triaxial accelerometers and gyroscopes in a small compact sensor device worn on a finger and ankle and will be used for the tremor and bradykinesia analysis. Subjects will follow motor tasks displayed on Kinesia's

touch screen tablet as the sensor data is captured and accessed from Kinesia's web application, which is a HIPAA-compliant online interface.

The Kinesia and Mobility Lab devices are FDA approved medical devices and are both commercially available.

During both study phases, participants will be assessed in the OFF medication state following overnight withdrawal of dopaminergic medications. They will be given 1.5 times their usual levodopa dose (up to 300mg) using Carbidopa/levodopa 25/100 tablet to ensure transition to the ON medication state. Carbidopa/levodopa 25/100 is widely used in treating PD and virtually all PD patients have taken it at some point in their treatment course. In addition, it is the drug of choice for the CAPSIT-PD, used for the preoperative assessment for deep brain stimulation.

Patients will return to the original DBS settings and medication regimen at the conclusion of each study visit.

6.1.2 DOSING AND ADMINISTRATION

During Phase I, participants will receive no stimulation. For those subjects with chronic DBS, their stimulators will be turned off for at least 50 minutes to ensure adequate "wash-out" of stimulation effects prior to the assessment in each condition. If symptoms become intolerable, the wash out period may be shortened. This will be determined by the PI on a case by case basis. During Phase II, the Lead Principal Investigator will reprogram each electrode contact pair in both 60Hz frequency and high frequency stimulation (HFS). For each of the 4 contacts on both electrodes, the amplitude will be slowly increased by 0.1-V/mA increment until sustained sensory or motor side effects are produced in HFS. The amplitude below the side effect threshold will be used along with a standard pulse width of 60 μ s.

In both Phases, participants will be assessed in the practically defined levodopa OFF condition--whereby they will have their overnight dopaminergic medications withdrawn--and the Levodopa ON condition, in which participants will be given 1.5 times their usual levodopa dose (up to 300mg) using carbidopa/levodopa 25/100 tablets with water.

SINEMET tablets are available in a 1:4 ratio of carbidopa to levodopa (SINEMET 25-100) as well as 1:10 ratio (SINEMET 25-250 and SINEMET 10-100). Tablets of the two ratios may be given separately or combined as needed to provide the optimum dosage. Studies show that peripheral dopa decarboxylase is saturated by carbidopa at approximately 70 to 100mg a day. Patients receiving less than this amount of carbidopa are more likely to experience nausea and vomiting. The optimum daily dosage of Sinemet must be determined by careful titration in each patient.

- This dosage schedule provides 75 mg of carbidopa per day.
- The patient should be informed that Sinemet is an immediate-release formulation of carbidopa/levodopa that is designed to begin release of ingredients within 30 minutes.
- All study participants will be on a levodopa regimen. They will be given 1.5 times their usual dopaminergic dose in the form of the study drug with 3 tabs being the maximum dosage. This is in line with the standard of care in assessing the transition of a Parkinson's patient from the OFF levodopa state to the ON state in a controlled setting.
- Study drug will be taken at the research site by mouth with water.

- Participants will be instructed to discontinue dopaminergic medications the night before each study visit, but they will remain on all other prescription medications. A drug-drug interaction is not anticipated during study participation with carbidopa/levodopa, as PD subjects, especially those with gait disorder, remain on some formulation of levodopa.
- Additional tablets will be administered (up to 1.5 times their usual dopaminergic dose) if wearing off is observed prior to the completion of study assessments.

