The opal body sensors (APDM, Opal, Portland, OR) will be fixed to each subject's wrists, ankles, sternum and lumbar spine and the SAW task will be carried out by the research coordinator for each combination of low and high frequency stimulation for the four contact pairs (total of 8 trials with each contact pair being either LFS or HFS, exclusively; refer to Figure 1). The gait measurements will be the same as in Phase I. Bradykinesia and tremor assessments will be conducted for each combination of stimulation and contact pairs using the Kinesia inertial sensors (Great Lakes Technologies, OH) as well. Ratings of items 3.1, 3.3 (a-e), 3.9, 3.11, 3.12, 3.13 of MDS-UPDRS III will also be conducted for each stimulation-contact pairing. Following each stimulation parameter change, there will be a 10-minute latency before the gait task is conducted. The participants will be blinded to each stimulation change.

During condition (2), the stimulators will be turned off and subjects will be given 1.5 times their usual levodopa dose (up to 300mg) to ensure transition to the medication ON state. Retesting will be done 1 hour after the levodopa challenge (or sooner based on patient report and visual confirmation by physician). Gait, bradykinesia and tremor sensor assessments as well as MDS-UPDRS III rigidity and axial subscore ratings will be conducted in the same manner as condition (1). The participants will be blinded to stimulation changes. At the completion of Visit 2, participants will return to their initial programming settings and resume their medication regimen as per their standard of care. If participant fatigue develops, he/she will have the option to complete condition (2) on another visit within a 4 week time period.

Beginning September 2020, and until the COVID-19 pandemic has passed, all subjects who are not fully vaccinated against COVID-19 will be tested for COVID-19 prior to participation (as outlined in Section 10.2). As a result, remote consent will be employed during the COVID-19 pandemic (see Section 8.2). COVID-19 tests will be performed by nasopharyngeal swab at a Northwell facility, the cost of which will be billed to the study fund.

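### Section 6.1.2 sets a three-tablet levodopa maximum and a 75 mg daily carbidopa figure that do not fit its own rule for additional tablets

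*Combined protocol and SAP*

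**What the plan says.** Section 6.1.2 (Dosing and Administration) describes the ON-state challenge: "participants will be given 1.5 times their usual levodopa dose (up to 300mg) using carbidopa/levodopa 25/100 tablets with water". Section 6.1.1 gives the same amount, and Sections 4.1 and 8.1 repeat it for both phases.

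The bullets in Section 6.1.2 then add three statements:

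- On the daily amount: "This dosage schedule provides 75 mg of carbidopa per day".
- On the limit: "with 3 tabs being the maximum dosage". No period is attached (administration, visit or day), and the multiplier of 1.5 is here applied to the usual dopaminergic dose.
- On re-dosing: "Additional tablets will be administered (up to 1.5 times their usual dopaminergic dose) if wearing off is observed". The base is again the usual dopaminergic dose.

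The analysis of Aim 1.2 (Section 9.4.2) represents medication by a single on/off indicator. Section 6.2.1 has administrations logged on a drug accountability form, but nothing ties an administration to a particular gait trial.

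**The concern.** The limit, the daily carbidopa figure and the re-dose rule stand in one bullet list, and for many plausible usual doses they cannot all be followed as written. Staff at a visit cannot tell whether three tablets is the ceiling for one administration or for the whole day. They also cannot tell whether the second multiple of 1.5 is a further allowance or a running total.

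This bears on safety. Section 2.3.1 names lightheadedness, nausea, hypotension and fatigue as possible effects of these tablets. Participants are selected for gait disorder and are asked to walk repeatedly after taking them.

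The analysis is affected less. Some ON trials may follow a second dose and others not, and the planned data would not show which.

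**Working it through.** **Inputs.** Each tablet holds 25 mg carbidopa and 100 mg levodopa. The challenge multiplier is 1.5, capped at 300 mg (Sections 6.1.1 and 6.1.2). The re-dose is up to 1.5 times the usual dose (Section 6.1.2). Phase II has eight trials per medication condition, with a 10-minute wait after each stimulation change (Section 4.1). The documents do not give participants' usual single levodopa dose, U, so it is an assumption here, shown from 50 to 300 mg. Amounts are nominal and not rounded to whole tablets.

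**The plan's own figure.** 3 x 25 = 75 mg carbidopa and 3 x 100 = 300 mg levodopa. The 75 mg statement reproduces, but as a single-dose amount only for one maximum dose with no additional tablets. At U = 100 mg, one challenge gives 150 mg levodopa and 150/4 = 37.5 mg carbidopa.

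**Totals after one full re-dose.** First dose = min(1.5U, 300). Carbidopa = levodopa/4. The text allows four readings:

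- (a) 1.5U is a running total: total = max(1.5U, first dose)
- (b) 300 mg caps the visit or day: total = min(first dose + 1.5U, 300)
- (c) 300 mg caps each administration: total = first dose + min(1.5U, 300)
- (d) the cap does not apply to the re-dose: total = first dose + 1.5U

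Levodopa/carbidopa in mg:

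| U | First dose | (a) | (b) | (c) | (d) |
|---|---|---|---|---|---|
| 50 | 75/18.75 | 75/18.75 | 150/37.5 | 150/37.5 | 150/37.5 |
| 100 | 150/37.5 | 150/37.5 | 300/75 | 300/75 | 300/75 |
| 150 | 225/56.25 | 225/56.25 | 300/75 | 450/112.5 | 450/112.5 |
| 200 | 300/75 | 300/75 | 300/75 | 600/150 | 600/150 |
| 250 | 300/75 | 375/93.75 | 300/75 | 600/150 | 675/168.75 |
| 300 | 300/75 | 450/112.5 | 300/75 | 600/150 | 750/187.5 |

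**What follows.**

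- U of 100 mg or less: one re-dose stays within three tablets and 75 mg on every reading. There is no conflict.
- U between 100 and 200 mg: only part of a full re-dose fits within three tablets.
- U of 200 mg or more: the first dose uses all three tablets, so any re-dose, however small, passes both three tablets in total and 75 mg.
- U above 200 mg: 1.5U exceeds 300 mg, so the re-dose as worded can exceed three tablets in a single administration.
- Reading (a) does not rescue the text. Up to U = 200 mg it leaves nothing to give as a re-dose, and above 200 mg the total passes 75 mg of carbidopa.

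**Is re-dosing likely to arise?** Section 4.1 sets a "total of 8 trials with each contact pair being either LFS or HFS, exclusively". The waits alone take 8 x 10 = 80 minutes, before walking, ratings and sensor tasks. Testing starts up to about an hour after the dose. The rule therefore covers a situation that can plausibly occur.

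**The case against.** The strongest reply is that the limits and the re-dose rule serve different purposes. The 300 mg limit qualifies the challenge that brings about the ON state, the three-tablet limit sits in the bullet about that transition, and the additional tablets answer a different trigger. On that reading the cap applies per administration and nothing prohibits a second dose. The 75 mg line also describes what the schedule supplies, after text about carbidopa being too low; it is not a ceiling.

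Much of this stands. Exceeding 75 mg shows an inaccurate sentence, not a breached safety limit. But the per-administration reading has to be supplied by the reader. It still leaves the 75 mg statement wrong after a full re-dose when U is above 100 mg, and the re-dose rule carries no cap of its own.

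A reader might infer four stronger points that the documents do not support:

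- **Three full doses in one day for chronic DBS participants.** Phase II can begin at visit 1, but its OFF condition requires overnight withdrawal, so a Phase I challenge earlier that day would break it. No section says that two separate challenges follow on one day.
- **A last ON trial at least 140 minutes after the dose (60 + 80).** Section 4.1 says "Retesting will be done 1 hour after the levodopa challenge (or sooner based on patient report and visual confirmation by physician", so the hour is not a minimum.
- **An undefined ON state.** ON rests on a levodopa challenge with a timing rule or clinical confirmation, and the re-dose is meant to maintain it.
- **A two-fold difference in exposure between early and late trials.** That treats cumulative tablets as concurrent effect, although the re-dose is given because the effect has waned.

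**Conclusion.** The contradiction is real and limited in extent. The three-tablet maximum, the 75 mg daily figure and the additional-tablet rule cannot all hold for participants whose usual dose is 200 mg or more if any re-dose is given, or for those above 100 mg if a full re-dose is given. For U = 300 mg, the text supports totals from 300/75 mg to 750/187.5 mg after one re-dose, depending on the reading. The change of base from levodopa to dopaminergic dose widens the ambiguity for anyone taking other dopaminergic drugs; Section 4.1 itself treats these as different quantities by converting PD medications to a levodopa equivalent.

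The result assumes that the usual dose means a single dose and that no more than one re-dose is given. The text sets no limit on repeats. How many participants are affected cannot be stated, because the documents give no distribution of usual doses.

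For Aim 1.2 the consequence is modest: ON trials may differ in dose history in a way that the on/off term cannot show. This does not invalidate the comparison.

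**What to change.** Reconcile Sections 6.1.1 and 6.1.2, and keep the matching text in Sections 4.1 and 8.1 aligned, so that five items agree: the cap, the period it covers, the additional-tablet rule including the number of repeats, the 75 mg statement, and the base dose to which 1.5 applies. The sponsor decides which rule applies; this review takes no position on the dose.

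Record the dose given and the time since the last dose against each ON trial, so that trials after a re-dose can be identified when Aim 1.2 is reported. Excluding those trials is not recommended. The protocol specifies no trial order, and re-dosed trials would tend to be the later ones, so exclusion could remove particular frequency and contact combinations and add order confounding.

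The cost is an amendment of wording and two extra fields on the case report form.

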6.2 PREPARATION/HANDLING/STORAGE/ACCOUNTABILITY

6.2.1 ACQUISITION AND ACCOUNTABILITY

The devices and drug identified as study interventions in this protocol will not be implanted or administered as investigational. Chronic DBS patients or patients planning to undergo DBS implantation are eligible for this study. Similarly, patients eligible for this study will already be taking levodopa as a part of their standard care for their Parkinson's disease. While this protocol does not intend to investigate the effects of Sinemet, this drug will be provided from an investigational supply.

Carbidopa/levodopa (brand name: Sinemet) 25/100 oral tablets will be acquired in bulk (100 count single dose blister packs) from the North Shore University Hospital Pharmacy via email order to [name], Rph or another NSUH pharmacist in [name] absence; the cost of which will be paid by study funds. Patient-specific prescriptions will *not* be utilized. Study drug will be acquired by a study coordinator and administered by [name]. The Northwell Drug Accountability Record Form template will be utilized to document lot#, expiration, administrations, disposal, etc. Unused drug will be disposed of via the North Shore University Hospital Pharmacy at the end of the study.

6.2.2 FORMULATION, APPEARANCE, PACKAGING, AND LABELING

Carbidopa/levodopa (brand name: Sinemet) 25/100 oral tablets. Tablets are yellow, oval, uncoated, that are scored and coded "650" on one side and "Sinemet" on the other side. Supplied in single dose blister packs, total count of 100. Sinemet is an FDA approved drug. No special preparation, randomization, packing, or other requests are required for this protocol.

6.2.3 PRODUCT STORAGE AND STABILITY

The kinesia and APDM mobility lab sensors will be stored in the Principal Investigators office in a locked cabinet. Carbidopa/levodopa (brand name: Sinemet) oral tablets will be stored at room temperature, protected from light, in the Principal Investigator's office in a locked cabinet and will be maintained in accordance with applicable investigational drug guidance.

